4.3 Tertiary/Exploratory Outcomes

- Legal guardian-reported PHQ-8 score at post-intervention
- Anxiety symptoms (GAD-7) at post-intervention
- Participant- and legal guardian-reported global functioning (PQ-LES-Q) at post-intervention
- Participant- and legal guardian-reported absenteeism at post-intervention
- Participant- and legal guardian-reported healthcare utilization at post-intervention
- Behavioral activation (BADS) at post-intervention
- Participant-reported app usability and engagement (SUS, UES-SF)
- Primary, secondary, and tertiary/exploratory outcomes at 1-month follow-up (as appropriate)

4.4 Intervention Compliance Outcomes

- Intervention adherence (rates of module and program completion) for SparkRx group
- App usage (daily active users, minutes spent in app) for SparkRx group

4.5 Safety Outcomes

- Number of adverse events (AEs), number of participants with AEs, and rates of AEs based on

- PHQ-8-based symptom deterioration and responses to weekly PSC questionnaires (both groups)
- Number of AEs, number of participants with AEs, and rates of AEs based on in-app freeform text (SparkRx group only)
- Number of adverse device effects (ADEs), number of participants with ADEs, and rates of ADEs (SparkRx group only)

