PIs along with the Medical Expert and study clinicians will provide continuous, close monitoring of all reported adverse events (AEs) and adverse device effects (ADEs). In compliance with IRB and DSMB guidelines, investigators will report adverse events and adverse device effects as required.

An adverse event is defined as any unwanted medical occurrence that occurs during the study. An adverse device effect (ADE) is an adverse event related to the use of an investigational medical device. This includes any adverse event resulting from insufficiencies or inadequacies in the instructions for use, the deployment, the installation, the operation, or any malfunction of the investigational medical device. This also includes any event that is a result of a user error or intentional misuse.

For this study, ADEs may occur in only the SparkRx arm.

An adverse event or adverse device effect is considered serious if it meets any of the following criteria:

- Is fatal;
- Is life-threatening, meaning, the participant was, in the view of the investigator, at immediate risk of death from the reaction as it occurred;
- Leads to persistent or significant disability/incapacity, i.e., the event causes a substantial disruption of a person's ability to conduct normal life functions;
- Requires or prolongs inpatient hospitalization;
- Is an important medical event, based on appropriate medical judgment, that may jeopardize the participant, or the participant may require medical or surgical intervention to prevent one of the other outcomes above.
 - Note 1: Planned hospitalization for a pre-existing condition, or a procedure required by the investigational protocol, without serious deterioration in health, is not considered a serious adverse event.
 - Note 2: Serious adverse device effect (SADE): adverse device effect that has resulted in any of the consequences characteristic of a serious adverse event.

The degree of certainty of causal relationship of an ADE to the mobile investigational device will be rated as follows:

- Not Possible: An event that is not due to the use of the study device. An alternative explanation, e.g., concomitant drug(s), concomitant disease(s) is clear.
- Possible: An event that might be due to the use of the study device. An alternative explanation - e.g., concomitant drug(s), concomitant disease(s) - is inconclusive. The relationship in time is reasonable; therefore, the causal relationship cannot be excluded.

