- Probable: An event that might be due to the use of the study device. An alternative explanation is less likely - e.g., concomitant drug(s), concomitant disease(s). The relationship in time is suggestive.
- Definitely: An event that is due to the use of the study device. The event cannot be reasonably

explained by an alternative explanation - e.g., concomitant drug(s), concomitant disease(s).

Unanticipated Adverse Device Effects (UADEs, as defined in 21 CFR 812.3, also referred to as “Unanticipated Problems”): Any serious adverse effect on health or safety or any life-threatening problem or death caused by, or associated with, a device, if that effect, problem, or death was not previously identified in nature, severity, or degree of incidence in the investigational plan or application; OR any other unanticipated serious problem associated with a device that relates to the rights, safety, or welfare of subjects.

UADEs must meet all the following criteria:

- Serious (as defined above)
- Associated with the device under investigation (possibly, probably, or definitely)
- Unexpected

No serious ADEs are expected. Given that psychotherapy and psychoeducation can lead individuals to think more about their depressive symptoms, expected ADEs may include temporary clinically significant deterioration in depressive symptoms and worsening mood. Anticipated AEs, given the study population, include suicidal ideation, non-suicidal self injury ideation, non-suicidal self injury (NSSI) that does not result in medical attention, clinically significant deterioration in depressive symptoms. Anticipated serious AEs that would be seen in this population independent of the study, include active nonsuicidal self injury resulting in medical attention, suicide attempts, death by suicide, and/or inpatient hospitalization unrelated to planned hospitalization for a pre-existing condition. Serious AEs will be reported biannually to the DSMB and to the IRB per local policy and as part of annual reporting unless they meet the definition of an UADE or unanticipated problem.

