The seriousness of an AE or ADE will be preliminarily determined by study clinicians, but final determination will be provided by an independent external clinician to eliminate bias in classification. All AEs must have their relationship to the investigational devices assessed by an external clinician based on the temporal relationship and his/her clinical judgment. The study clinicians and Medical Expert will be responsible for determining whether an ADE is expected or unexpected. An ADE will be considered unexpected if the nature, severity, or frequency of the event is not consistent with the risk information previously described for the study intervention.

All AEs, ADEs, and complaints will be recorded. The external clinician and the Medical Expert will determine whether it is in the participant's best interest to remain in the study after any serious AE or UADE and notify the PI accordingly.

Study PIs will report UADEs to the IRB and DSMB within 10 working days. Limbix will immediately conduct an evaluation of any reported UADEs and will report such effects to the FDA within 10 working days. If it is determined that an UADE presents an unreasonable risk to subjects, the investigation or parts of the investigation presenting that risk will be terminated as soon as possible. Termination shall occur not later than 5 working days after the sponsor makes this determination and not later than 15 working days after the sponsor first receives notice of the effect. Limbix will not resume a terminated investigation without IRB approval and, if the investigation was terminated under paragraph (b)(2) of 21 CFR 812.46, FDA approval.

Per 21 CFR 56.108(b)(1) and 21 CFR 812.150(a)(1), PIs will report any unanticipated problem involving risk to human subjects or others to the IRB no later than 10 business days from the time of identification. An unanticipated problem must meet all the following criteria:

- Unexpected (in terms of nature, severity, or frequency) given the information provided in research-related documents and the characteristics of the subject population being studied;
- Related or possibly related to participation in the research; AND
- Suggests that the research places subjects or others at a greater risk of harm than was previously

known or recognized.

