4.8.1 Study Staff Responsibilities

If suicide ideation is endorsed at any point during the study, a safety protocol will be initiated. If participants are found to have a high suicide risk, they will be excluded from the research study and participants will be directed to appropriate local resources. A participant has high risk for suicide if they endorse ideation with a plan or intent. All safety incidents will be documented and reported to the DSMB, IRB, and FDA as needed.

If safety risks related to suicidality are identified during a study session, a brief suicide screening assessment (e.g., Self-Injurious Behavior Thoughts and Behavior Interview (SIBTI) may be conducted (Appendix 7). If there is an immediate concern for safety, the participant will be directed to go to the nearest ER or call 911/local behavioral health emergency responders. The study clinician will be alerted and triage safety risk as per the study safety protocol. The study clinician will contact the participant and emergency contact as needed, provide resources, and determine whether additional steps are necessary.

Symptom deterioration will be defined as a PHQ-8 score ≥ 15 and a ≥ 5 -point increase from baseline or a PHQ-8 score ≥ 20 at two consecutive timepoints. If a deterioration event occurs, an alert will be sent to the study team. Freeform text entered in the mobile app, PSC assessments, and deterioration alerts will be reviewed by study staff daily. Any correspondence from a study participant will also be reviewed. If a safety concern is identified (including endorsements of or thoughts of self-harm, harming others, or others are harming them), a study team member will notify a study clinician. The contacted study clinician will review all deterioration events and concerning freeform text and reach out to participants and emergency contacts if indicated, as per the study safety protocol. The Medical Expert clinician will determine the outcome of adverse events and unanticipated adverse device effects in consultation with the independent external clinician. Data about individual safety concerns, AEs, ADEs, and outcomes of clinical reachout may be securely shared with participants' healthcare provider or referring healthcare system upon written authorization by the participant and/or legal guardian as part of the informed consent process.

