The DSMB will meet (e.g. teleconference) prior to the start of intervention to review and provide recommendations regarding the research protocol, informed consent/assent documents, and plans for data safety and monitoring. Subject recruitment will be initiated after review of the study protocol by the DSMB. The DSMB will then meet on a biannual basis or twice during the study duration to assess data quality and timeliness, participant recruitment, accrual and retention, participant risk versus benefit, any breaches of confidentiality, as well as the ethics of this trial. Detailed information will be provided to the DSMB prior to each of the scheduled meetings. This report will include a range of information on study procedures, measures, family responses, methodology, and acceptability of the intervention and measures, as well as AEs, ADEs, and SAEs experienced by study participants. Data on study progress and protocol integrity will be provided to the DSMB to ensure that the study is moving forward as planned. The DSMB Chairperson may convene additional meetings when deemed necessary.

Within 2 weeks of meeting, the DSMB will provide a written report of their recommendation to the study PIs including any modifications and recommendations. The DSMB will also make recommendations at any time to the sponsor (Limbix), the NIMH (as deemed necessary), and the study PIs concerning continuation, termination, or other modifications of the trial based on the observed beneficial or adverse effects of the trial. Any recommended changes or adjustments about the study will be considered. If it is determined that the recommendations cannot be followed, the sponsor and study PIs will provide an explanation of why they cannot be followed to the DSMB and the NIMH. The IRB will receive a blinded summary report of safety findings on an annual basis from the study PIs. This data and safety review as well as an assessment of protocol compliance and data quality will facilitate the early detection of safety signals and will maximize the likelihood of continued appropriateness of the research and protection of human subjects. The review will also ensure that participants who experience AEs are provided with proper and, if necessary, ongoing attention. Any recommendations to improve participant safety, protocol adherence, or data quality will also be included.

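### The only adverse-event outcome covering both arms in section 4.5 is limited by source, so events the trial has recorded, including serious ones, can fall outside it

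*Combined protocol and SAP*

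**What the plan says.** Section 4.5 of the combined protocol and SAP lists three safety outcomes. Each asks for a number of events, a number of participants and a rate.

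- **AEs, both arms.** Rejoined across a line break, the first item bases the count on "PHQ-8-based symptom deterioration and responses to weekly PSC questionnaires (both groups").
- **AEs, SparkRx only.** "Number of AEs, number of participants with AEs, and rates of AEs based on in-app freeform text (SparkRx group only").
- **Adverse device effects (ADEs), SparkRx only.** "Number of adverse device effects (ADEs), number of participants with ADEs, and rates of ADEs (SparkRx group only"). No source is named here.

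Serious AEs have no line of their own.

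Sections 4.8 and 4.8.1 are broader. "An adverse event is defined as any unwanted medical occurrence that occurs during the study", and "All AEs, ADEs, and complaints will be recorded". Review of incoming information goes beyond questionnaires and free text: "Any correspondence from a study participant will also be reviewed". Section 4.8 also names the serious events to be expected in this population, among them "suicide attempts, death by suicide, and/or inpatient hospitalization unrelated to planned hospitalization for a pre-existing condition".

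**The concern.** The definition and the recording rule cover every AE, while the one outcome that can be set side by side for the two arms covers only AEs that arrive by two routes. A table built to the letter of 4.5 could leave out a suicide attempt, an admission or a death that the trial knows about and has classified, simply because nobody reported it on a weekly PSC. Section 1.1 makes safety, judged by AEs and ADEs, one of the outcomes of the study. In a trial of 13- to 21-year-olds with depressive symptoms, the serious events are the ones a reader will look for first.

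**Working it through.** The plan attaches no figure to its safety outcomes, so there is nothing to reproduce. The check compares sections and then counts PSC timepoints.

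**1. Does another section widen 4.5?** Section 4.7 has subsections on the general approach and on primary, secondary, tertiary/exploratory and compliance outcomes, but none on safety. Section 4.3 carries primary, secondary and tertiary outcomes to 1 month and does not name safety outcomes. The reports to the DSMB described in 4.8.1 are wider, "as well as AEs, ADEs, and SAEs experienced by study participants", but a DSMB report is not a trial outcome by arm. Nothing widens 4.5.

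**2. Which routes are inside the two-arm count?**

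| Route by which an event can become known | In the two-arm AE count of 4.5? |
|---|---|
| PHQ-8 deterioration, any scheduled PHQ-8 | Yes |
| Participant PSC, weekly | Yes |
| Guardian PSC, weekly (under 18 only) | Yes; 4.5 does not restrict the PSC to participants |
| Participant or guardian PSC, post-intervention and 1 month | Unclear (step 4) |
| Participant correspondence | No |
| Emergency contact or provider | No |
| SparkRx free text | No; counted separately |

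**3. Whose events are most likely to be missed?**

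- *Adults.* Table 1 gives guardian versions only for those under 18. Section 2.3 aims for equal representation under and over 18. If that target is met among the 220 enrolled, 220 / 2 = 110 participants have no guardian PSC.
- *Participants removed from the study.* Section 4.8.1 excludes those found at high suicide risk. Section 3.1 closes the app and the portal at once for anyone who withdraws, or who is dropped during the 5 weeks. I take exclusion under 4.8.1 to be a form of being dropped. After that point the participant has no PSC to answer, so a later event could become known only by a route that 4.5 does not list. The text does not say whether a guardian's portal account closes too.

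**4. How much of the PSC schedule is in doubt?** Section 4.6 counts six PHQ-8 measurements, baseline plus weekly, so 6 - 1 = 5 weekly timepoints. Section 3.1 has the PSC prompted alongside the weekly PHQ-8. Table 1 adds a PSC at post-intervention and one at 1 month.

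- Scheduled PSC timepoints: 5 + 2 = 7.
- Outside a strict reading of weekly: 2 / 7 = 29%.

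For the strict reading: Table 1 has a separate column for the weekly assessments, and section 3.4 puts them in the app but the later ones in the portal. Against it: section 3.1 speaks of weekly PSCs as a general name for the instrument. The text does not settle which is meant.

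**5. Does deterioration after week 5 still count?** Yes. Section 4.8.1 defines it from PHQ-8 scores with no limit to weekly ones, and Table 1 schedules the PHQ-8 at post-intervention and 1 month.

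**The case against.** The strongest reply is that this is a matter of wording. Every AE is recorded, seriousness is finally judged by an independent clinician, serious AEs go to the DSMB, section 1.1 states the safety outcome without any limit of source, and section 4.7 promises a detailed SAP that can put the table right. All of that stands. It means no data are lost; it does not change what 4.5 now tells the analyst to count.

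A reader might also infer more than the documents support:

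- *That the two-arm count favours one arm because the sources differ.* It does not. That count uses the same sources in both arms. Free text and ADEs are in separate items, and 4.8 confines ADEs to SparkRx by definition.
- *That events are counted twice.* Nothing says the three items are added together, so an event may properly appear in more than one.
- *That serious AEs are not counted at all.* A serious AE reported on a weekly PSC is an AE and is counted. What is missing is a separate line, and those that come by other routes.
- *That deaths and admissions escape the PSC almost entirely.* For minors the weekly guardian PSC is a listed route. The PSC also asks about the time since the last check, so a participant discharged after a short stay can report it later.
- *That about half of follow-up is unobserved.* With 5 + 4 = 9 weeks, or 11 with the 2-week completion window, the time after week 5 is 4/9 = 44% to 6/11 = 55%. Those figures assume the strict reading of weekly and observation counted from baseline, and they do not apply to PHQ-8 deterioration.
- *That the trial cannot support a safety conclusion.* No between-arm safety test is specified, and the full record exists.

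**Conclusion.** The point holds in a limited form. The two-arm AE outcome in 4.5 is narrower than the plan's own definition and recording of AEs, no other section repairs this, and there is no separate serious-AE outcome. Followed literally, it can omit serious events that the trial has recorded. This conclusion does not depend on how weekly is read.

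The treatment of the post-intervention and 1-month PSC (2 of 7 timepoints) is an ambiguity to resolve, not a demonstrated exclusion.

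The number of events affected is unknown: the documents give no expected event rates and no split by route of report. The argument about removed participants assumes that exclusion for suicide risk triggers the access restriction in 3.1. The efficacy results and the sample size are unaffected.

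**What to change.** Reword 4.5, and carry the wording into the detailed SAP:

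1. **Main safety outcome:** all recorded AEs and, on a separate line, all serious AEs, by randomised arm, from any source, from randomisation to the 1-month assessment. Give numbers of events and of participants, with each event counted once in this total.
2. **Like-for-like comparison:** keep the existing count from PHQ-8 deterioration and the participant and guardian PSC, and state that it includes the post-intervention and 1-month PSC.
3. **Free text:** continue to report events from this source separately for SparkRx.

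The cost is wording and one further table; events and their seriousness are already recorded. The downside is unequal detection in the any-source count, since only SparkRx has free text. The shared-source count stays beside it for that reason, and the report should say so.

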4.6 Sample Size

Sample size calculation is based on primary outcome PHQ-8 at post-intervention. Six PHQ-8 measurements will be collected from each subject (baseline and weekly during the 5-week intervention period). Using a two-sample t-test approach, assuming a two-tailed alpha set at 0.05, a total of 200 participants (100 in each study arm) will give us 80% power to detect a moderate effect size of at least $d=0.4$. Given an anticipated 10% rate of attrition, we aim to enroll 220 total participants in the study.

4.7 Data Analysis

Detailed statistical analysis plans (SAP) will be developed prior to completion of primary outcome data collection. Prior to analysis, study population details including the number randomized to each study arm and lost to follow-up will be described. Baseline participant characteristics will be summarized for the SparkRx and eUC arms as means, standard deviations, medians, 25th and 75th percentiles for continuous variables, and as counts and percentages for categorical variables. Differences in baseline characteristics between the groups will be explored using tabular and visual displays, as appropriate, and appropriate statistical tests (e.g., independent sample t-tests for continuous variables, chi-square tests for categorical variables).

4.7.1 General Approach

Analysis Populations: All analyses will be completed in line with the intention-to-treat (ITT) principle, where all participants will be included in the analyses according to their assigned study arm at baseline, regardless of adherence to study protocol. Per-protocol analyses will also be conducted to estimate treatment effects for participants who adhered to the protocol, and will include individuals who completed the Baseline and post-intervention PHQ-8 assessments and, for participants in the SparkRx group, met a minimum engagement threshold of completing two modules.

Descriptive Statistics: For descriptive statistics, the following will be reported:

Continuous data: n, mean, standard deviation, median and interquartile range, minimum and maximum

Categorical: n/N and percentage of total per arm

Missing Data: We do not anticipate missing data for the stratification variables, which will be included as covariates in the analysis models. Ongoing efforts will be made to reduce the amount of missing data for all outcomes. Despite these efforts, missing data for primary, secondary, and tertiary/exploratory outcomes are likely. Data missing at random (MAR) on dependent variables are easily handled in repeated measures mixed models so no imputation will be needed. For all other statistical analyses described below and missing data on covariates (or independent variables) in models, multiple imputation will be used if at least 5% of data points are missing for a given covariate or variable. Case analysis or single imputation methods may also be used and a specific approach for imputation will be selected based on key attributes of the obtained data, including percent missing and whether data are missing at random. We will compare the results obtained with and without imputation. Sensitivity analyses will be used to assess the impact of potential deviations from the MAR assumption on the study findings.

